Appendix 1:

Data Safety Monitoring Board (DSMB) Reports:

1.1 Immediate reports:

Refers to reports of any for Fatal or Life-Threatening Suspected Unexpected Serious Adverse Reactions (SUSARs). These reports should include basic information (e.g. date of vaccination and vaccine lot) and data from the CRF Serious Adverse Events case report form. As indicated in the SOPs WHO 1-3 reporting should take place immediately – within 24 hours- of first knowledge by CMC.

1.2 Regular reports (every 3 months):

These reports contain basic information regarding progress with recruitment (Table 1.2.1). A histogram chart was proposed to illustrate the information on the proposed table (Figure 1.2.1). An aggregated information on Fatal or Life-Threatening Suspected Unexpected Serious Adverse Reactions (SUSARs) to vaccination is given (Table 1.2.2A and Table 1.2.2B). Information will be shown by study arm (Aerosol or SQ), type of adverse event and time of onset after vaccination. The laboratory results will be provided only if requested by the DSMB.

SOP VEL 1/1:	Statistical Analysis Plan	Page 49 of 61
Sep 2012		

Phase II/III Clinical TrialWHO Measles Aerosol Vaccine ProjectProtocol WHO/MAP/IN/002
--

 Table 1.2.1: Number of children enrolled and vaccinated by study area, study arm, sex

Study area	Assess for	Allocated to	Received allocated	Aeı	osol A	rm	Subcutaneous Arm			
	eligibility	Intervention	Intervention	Boys	Girls	Total	Boys	Girls	Total	
1.										
2.										
3.										
4.										
5.										
6.										
7.										
8.										
TOTAL										

Remarks:

The median age of children at randomisation was (inter	erquartile ranget	to d	lays) (range	to	days).
--	-------------------	------	--------------	----	--------

SOP VEL 1/1:	Statistical Analysis Plan	Page 50 of 61
Sep 2012		

Phase II/III	WHO Measles Aerosol Vaccine	Protocol
Clinical Trial	Project	WHO/MAP/IN/002

Figure 1.2.1: Histogram for Table 1.2.1 data

SOP VEL 1/1:	Statistical Analysis Plan	Page 51 of 61
Sep 2012		

Phase II/III	WHO Measles Aerosol Vaccine	Protocol
Clinical Trial	Project	WHO/MAP/IN/002

Table 1.2.2A: Frequency of Fatal or Life-Threatening Suspected Unexpected Serious Adverse Reactions (SUSARs) by study group and time since vaccination

Part 1: Serious Adverse Events

							Ti	me sino	ce vaccii	nation								То	tal
Name	Vis	sit 2	V	isit 3	Vis	Visit 4		Visit 5		Visit 6		Visit 7		sit 8	Visit 9		••		
	0 - 30) mins	31 mins – 3 days		4 – 7 days		8 – 10 days		11 – 14 days		15 – 16 days		17 – 2	1 days	22 – 28 days				
	AER	SC	AER	SC	AER	SC	AER	SC	AER	SC	AER	SC	AER	SC	AER	SC		AER	SC
Serious Adverse																			
Events**																			
Result in death																			
Is life																			
threatening																			
Results in																			
persistent or																			
significant																			
disability or																			
incapacity																			
Requires																			
hospitalization																			
or																			
continuation																			
of existing																			
hospitalization																			
Important																			
medical event																			
Total																			

SOP VEL 1/1:	Statistical Analysis Plan	Page 52 of 61
Sep 2012		

Phase II/III	WHO Measles Aerosol Vaccine	Protocol
Clinical Trial	Project	WHO/MAP/IN/002

Part 2: Unexpected Adverse Events

		Time since vaccination																	
Name	Visit 2 0 – 30 mins		Visit 3 31 mins – 3 days		Visit 4 4 – 7 days		Visit 5 8 – 10 days		Visit 6 11 – 14 days		Visit 7 15 – 16 days		Visit 8 17 – 21 days		Visit 9 22 – 28 days			Total	
	AER	SC	AER	SC	AER	SC	AER	SC	AER	SC	AER	SC	AER	SC	AER	SC		AER	SC
Unexpected Adverse Events**																			

SOP VEL 1/1:	Statistical Analysis Plan	Page 53 of 61
Sep 2012		

Phase II/III	WHO Measles Aerosol Vaccine	Protocol
Clinical Trial	Project	WHO/MAP/IN/002

Part 3: Severe Adverse Events

							I	Time si	nce vaco	cination	L								
Name	Vis 0 – 30	it 2 mins	Vis 31 mi da	it 3 ns – 3 sys	Vis 4 – 7	it 4 days	Vis 8 – 10	it 5 days	Vis 11 – 14	it 6 4 days	Vis 15 – 10	it 7 6 days	Vis 17 – 2	it 8 1 days	Vis 22 – 2	it 9 8 days	••		sc
Severe	ALA	bC.	ALA	50	ALA	BC	ALA	50	ALA	BC	ALA	BC	ALA	BC	ALA	sc		ALA	BC
Adverse																			
Events***																			
Anorexia																			
Conjunctivitis																			
Coryza																			
Cough																			
Crying																			
Diarrhoea																			
Difficulty																			
breathing																			
Fever																			
Irritability																			
Local																			
Malaise																			
Rash																			
Seizure																			
Shivering																			
Vomit																			
Wheeze																			
Others																			
Total																			

SOP VEL 1/1:	Statistical Analysis Plan	Page 54 of 61
Sep 2012		

Phase II/III	WHO Measles Aerosol Vaccine	Protocol
Clinical Trial	Project	WHO/MAP/IN/002

Table 1.2.2B: Frequency of Fatal or Life-Threatening Suspected Unexpected Serious Adverse Reactions (SUSARs) that have been deemed*probably related* and *most probably related* to vaccination* by study group and time since vaccination**Part 1:** Serious Adverse Events

								Time si	nce vaco	cination	l								
Name	Vis 0 - 30	it 2) mins	Vis 31 mi da	it 3 ns – 3 ys	Vis 4 – 7	it 4 days	Vis 8 – 10	it 5) days	Vis 11 – 14	it 6 4 days	Vis 15 – 1	sit 7 6 days	Vis 17 – 2	it 8 1 days	Vis 22 – 2	it 9 8 days	••	То	tal
Contours A drugues	AER	SC	AER	SC	AER	SC	AER	SC	AER	SC	AER	SC	AER	SC	AER	SC		AER	SC
Serious Adverse																		l l	
Events**																		l l	
Result in death																		ľ	
Is life																			
threatening																			
Results in																			
persistent or																		l l	
significant																		l l	
disability or																		l l	
incapacity																			
Requires																			
hospitalization																		l l	
or																		l l	
continuation																		l l	
of existing																		l l	
hospitalization																		ļ!	
Important																		l l	
Tetal																		ļ!	
SOP VEL 1/1: Sep 2012			Stat	istical	Analysi	s Plan				Page	55 of 6	51							

Phase II/III	WHO Measles Aerosol Vaccine	Protocol
Clinical Trial	Project	WHO/MAP/IN/002

Part 2: Unexpected Adverse Events

		Time since vaccination																	
Name	Vis 0 - 30	sit 2) mins	Vis 31 mi da	Visit 3 31 mins – 3 days		Visit 4 4 – 7 days		Visit 5 8 – 10 days		Visit 6 11 – 14 days		Visit 7 15 – 16 days		sit 8 1 days	Visit 9 22 – 28 days			Total	
	AER	SC	AER	SC	AER	SC	AER	SC	AER	SC	AER	SC	AER	SC	AER	SC		AER	SC
Unexpected Adverse Events**																			

SOP VEL 1/1:	Statistical Analysis Plan	Page 56 of 61
Sep 2012		

Phase II/III	WHO Measles Aerosol Vaccine	Protocol
Clinical Trial	Project	WHO/MAP/IN/002

Part 3: Severe Adverse Events

							r	Fime si	nce vaco	cination	l								
Name	Vis 0 - 30	Visit 2 0 – 30 mins		Visit 3 31 mins – 3 days		Visit 4 4 – 7 days		Visit 5 8 – 10 days		Visit 6 11 – 14 days		Visit 7 15 – 16 days		sit 8 1 days	Visit 9 22 – 28 days		••	Total	
	AER	SC	AER	SC	AER	SC	AER	SC	AER	SC	AER	SC	AER	SC	AER	SC		AER	SC
Severe Adverse Events*** Anorexia																			
Conjunctivitis																			
Coryza																			
Cough																			
Crying																			
Diarrhoea																			
Difficulty																			
Fever																			
Irritability																			
Local reaction																			
Malaise																			
Rash																			
Seizure																			
Shivering																			
Vomit																			
Wheeze																			
Others																			
Total																			1

* 1. Not related 2.unlikely to be related 3.Possible 4. Probable 5. Most probably 6. Insufficient data to assess

** 1. Results in death 2. Is life threatening 3. Results in persistent or significant disability or incapacity 4. Requires hospitalization or continuation of existing hospitalization 5. Important medical event (may not result in death but may jeopardise subject)
 *** As defined in the protocol list of solicited adverse events

SOP VEL 1/1:	Statistical Analysis Plan	Page 57 of 61
Sep 2012		

17. Additional Analyses

17.1. Sero-positivity at Day91: By Vaccinated Sequential Number

17.1.1. Difference in Sero-positivity between study arms by Vaccination Sequential Number

Table17.1.1.1: Measles seropositive at day 91 post-vaccination (all infants) and difference in positivity between study arms by Vaccination Sequential Number

Seropositive at Day91, by VacSeqNo	AER n/N	AER% 95% CI	SC n/N	SC% 95% CI	Difference (AER-SC) 95% CI
1					
2					
3					
4					
5					
6					
7					
8					
9					
10					

Legend: AER-aersol; SC-subcutaneous;

*This difference is used to interpret non-inferiority, estimated by Wilson score method.

SOP VEL 1/1:	Statistical Analysis Plan	Page 58 of 61
Sep 2012		

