6.3.1.2 Sequence generation

The allocation sequence will be computer-generated random numbers, in permuted blocks, generated by an independent statistician. The randomization ratio will be 1:1.

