6.7.1.1 Vaccine Storage, Handling and Transport

The vaccine will be stored, according to the manufacturer's recommendations at $2^{\circ}C$ to $8^{\circ}C$ in a refrigerator in which the temperature is monitored and logged at least once a day. The refrigerator will be secured and located in a limited access area.

6.7.2 Policy and procedure for handling unused investigational product.

(SOP WHO 4/1))

- All unused un-reconstituted measles vaccine will be disposed of according to the manufacturers instructions and WHO³³.
- All reconstituted vaccine not used within 6 hours after reconstitution during an immunization session will be discarded according to WHO recommendations for multi dose open vials.⁴¹ Records will be kept of discarded vaccine.
- All non-reusable components of the nebulizer will be disposed of as indicated in SOP NEK 2/1
- The nebulizers used during the trial will be returned to the sponsor at the end of the trial according to sponsor-defined procedures.

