When a unique study ID has been confirmed the person clicks the 'Randomization' button. The next screen gives the allocation as either, 'AEROSOL' or 'SUBCUTANEOUS'. The system records, in a separate database, the details of study site, child's names, Subject ID number, allocation, date and time of randomization. The randomization database will be maintained in Access as backend. This database will be maintained at the CDMC and the backup will be maintained at the backup server which is kept at the Pharmacology Department Museum (old name: Booshnam Moses Computing Center) (Refer SOP Randomization, No: 05 / 02).

SOP VEL 1/1:	Statistical Analysis Plan	Page 5 of 61	
September 11, 2012			

7.3 Blinding of Laboratory Staff:

Staff at the study sites and participants' parents will know which treatment has been given. To minimize bias in the assessment of immunogenicity outcomes, laboratory staff will not know the treatment allocation or the order of specimens that they will analyze.

In order to blind laboratory staff to the specimen collection time (day 0, day 28 day 91 or day 364) for the subjects, a single digit random number will be generated and concatenated with the subject ID. This is called the Lab Code. Thus a subject will have a unique Lab Code of 5 digits.

The laboratory will be provided with lists of 22 pairs (day 0 and day 91) of specimen Lab Codes, which will be randomly ordered. Similarly, for the specimens of children who will be followed up at day 28 and day 364, the laboratory will be provided with lists of randomly ordered Lab Codes.

8.0 Sample size:

8.1 Immunogenicity:

The sample size for the primary outcome is determined using the confidence interval (CI) approach, considering where the CI for the treatment effect lies with respect to a pre-specified margin of non-inferiority and the null effect (1).

Total to be enrolled, 2000. This number was based on the following assumptions:

- Significance 2.5%, one sided for non-inferiority, 5% for two sided superiority;
- Non-inferiority margin 5%;
- Power for non-inferiority 90% if true seropositivity is 90% in both arms;
- 20% loss to follow up by day 91, leaving 1600 available for primary analysis.

Sample size for immunogenicity subset:

Those selected for additional testing at day 28 or at day 364 will have ELISA and PRNT test results at these time points as well as at day 0 and 91.

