Baseline: Age in months, sex, usual health care provider, heart rate, respiratory rate, temperature, height for age, weight for age, any abnormality discovered on systemic examination, pre existing medical conditions (Table 11.12.6.1B)

Others: Observations during vaccination (Table 11.12.6.1D)

The distribution of the baseline covariates by study arm will be described, but not formally tested as randomization will have ensured that any differences are chance differences. For the main comparison of the study arms adjustment for these covariates is not necessary. To investigate the effect of these covariates on study end-points multivariable logistic regression (for binary end points) or normal errors regression (on logged antibody levels) will be performed. Study arm will be included in these analyses and interactions examined as given in section 11.11.

11.10 Sub-group analyses:

No sub group analyses have been planned.

11.11 Interactions with study arm:

Potential interactions will be examined for the following co-variates: sex, age, crying during measles vaccination, and acute respiratory infection.

11.12 Descriptive Analyses:

11.12.1 Distributions of continuous variables and any agreed transformations:

Mean, standard deviation, median, and interquartile range will be generated for continuous variables. The PRNT values will be doubled if the value is >20,000. The PRNT values will be \log_{10} transformed for further analyses such as GMT and 95% CI. Results at the lower limit of the assay will be assigned a value of 10. OD values will also be \log_{10} transformed to calculate geometric means and perform regression. Any OD results of <0.01 will be assigned a value of 0.005 prior to \log_{10} transformation.

11.12.2 Distributions of binary and categorical variables:

Frequency distributions will be shown for binary and categorical variables. The categories will be checked against the Annotated CRF.

11.12.3 Outliers:

For \log_{10} PRNT values, checks for outliers will be performed prior to the statistical analysis as part of the data checking. The outliers will also be examined using standardized residuals >3 when looking at \log_{10} PRNT values.

SOP VEL 1/1:
September 11, 2012

Phase II/III	WHO Measles Aerosol Vaccine	Protocol
Clinical Trial	Project	WHO/MAP/IN/002

11.12.4 Flow of Numbers:

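### Two additional SAP tables read non-inferiority row by row, by vaccination sequence number and by site, where equal vaccines would usually miss the margin; any trend across sequence numbers is left untested

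*Supplement*

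**What the plan says.** SAP 17.1.1 tabulates day-91 seropositivity in ten rows, Vaccination Sequential Number 1 to 10. Each row gives n/N and a percentage with 95% CI for each arm, then the aerosol-minus-subcutaneous difference with its 95% CI. The legend reads "This difference is used to interpret non-inferiority, estimated by Wilson score method". Table 17.2.1.1 has the same columns and legend for eight study areas. The same sentence stands under Table 12.1.3, the overall primary comparison.

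SAP 11.1 and Protocol 12.1.2 define the decision rule once, for the whole trial: non-inferiority is concluded if the lower limit of the two-sided 95% CI for the difference lies above -5%. SAP 8.1 sizes the trial for that single comparison, assuming "Power for non-inferiority 90% if true seropositivity is 90% in both arms". Its allowance for infants who drop out is given separately as "20% loss to follow up by day 91, leaving 1600 available for primary analysis".

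SAP 11.10 states "No sub group analyses have been planned". Sequence number does not appear among the covariates (11.9), the interactions (11.11) or the risk-factor model (12.3), and the SAP does not define it. Protocol 6.4.2 lists 10-dose vials for both arms. Protocol 6.7.2 says "All reconstituted vaccine not used within 6 hours after reconstitution during an immunization session will be discarded".

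**The concern.** The legend ties the trial's decision rule to rows that hold a small fraction of the sample. A reader who follows it would report that non-inferiority was not shown at most sequence numbers and most sites, and could take this as evidence of a problem with late doses or particular health centres when only sample size is at work.

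There is a second, smaller gap. If the sequence number is the order in which doses were drawn from a vial, the natural question is whether response falls from the first dose to the tenth. The only planned contrast compares the arms at the same position, so its expected value is zero whenever both arms decline alike. No trend test and no arm-by-sequence interaction is planned.

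**Working it through.** **Inputs**
- Margin: SAP 8.1, "Non-inferiority margin 5" percentage points.
- Error rate: "Significance 2.5%, one sided for non-inferiority, 5% for two sided superiority".
- True rate: 90% in both arms (SAP 8.1).
- Size: 1600 evaluable; "The randomization ratio will be 1:1" (Protocol 6.3.1.2), so 800 per arm.
- Interval: Wilson score (SAP 11.1), taken as the Newcombe interval for a difference.
- Row size: 800/10 = 80 per arm on average. Even spread is an assumption; 40 to 160 per arm is shown as a range.

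**1. The plan's own power.** By the normal approximation, power = Φ(margin/SE − 1.96), with SE = √(2 × 0.9 × 0.1/n). For n = 800, SE = 0.015 and power = Φ(3.333 − 1.96) = 91.5%. Exact binomial enumeration of the Newcombe-Wilson rule gives 91.3%. The planned 90% is reproduced.

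**2. The same rule in one row of 80.** Now SE = √(0.18/80) = 0.0474 and the approximation gives Φ(1.054 − 1.96) = 18.3%. Exact enumeration gives 16.5%.

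The lower limit is (pA − pS) − √[(pA − lA)² + (uS − pS)²], where l and u are the Wilson limits of each proportion. With 72/80 observed in both arms, l = 0.815 and u = 0.948, so the half-width is √(0.085² + 0.048²) = 0.098. The lower limit is −9.8 points, nearly twice the margin, although the arms are identical. To pass, a row near 90% needs aerosol ahead by roughly 5 points.

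**3. Chance that a row meets the margin when the vaccines are equal (exact)**

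| Per arm in row | True rate 85% | 90% | 95% | 97% |
|---|---|---|---|---|
| 40 | 8% | 9% | 12% | 11% |
| 80 | 14% | 16% | 23% | 30% |
| 100 | 17% | 20% | 31% | 41% |
| 160 | 24% | 31% | 49% | 65% |
| 800 (whole trial) | 80% | 91% | 99% | >99% |

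For the site table, 800/8 = 100 per arm on average (even spread again assumed), so a row meets the margin about 20% of the time at 90%.

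**4. All ten sequence rows.** At 80 per arm and 90%, the expected number of passes is 10 × 0.165 = 1.6. The chance that all ten pass is 0.165¹⁰, about 1.5 × 10⁻⁸. At a true rate of 97% it is 0.3045¹⁰, about 7 × 10⁻⁶.

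**5. What a trend test would offer.** I simulated a linear-trend (Cochran-Armitage) test in one arm of 800 at two-sided 5%. The declines are assumed; the documents give none. The uneven spread is illustrative: 152 infants at position 1, falling by 16 per position to 8 at position 10.

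| Assumed fall, position 1 to 10 | Even spread | Sparse late positions |
|---|---|---|
| 95% to 85% | 86% | 76% |
| 95% to 90% | 40% | 32% |

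**The case against.** The strongest reply is that the legend is a carry-over. In Table 12.1.3 an asterisk in the difference column anchors it; in 17.1.1.1 and 17.2.1.1, as shown, no column refers to it. Both tables sit under Additional Analyses, SAP 11.7 uses no fixed significance level for additional analyses, and the decision rule is one overall interval. All of this stands. A reader might infer that the trial's verdict could turn on these rows; the documents do not support that.

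A reader might also infer that a fall in potency across the vial would go unseen. It need not: the table prints each arm's percentage and CI at every sequence number, so a decline would be visible down those columns. Only the difference column cancels a shared decline. What is missing is a formal test.

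Nor do the documents say that the table was meant to check vial potency. Reading the number as vial position is an inference from its range of 1 to 10 and the 10-dose vials. How often vials were emptied is not stated either, so 80 per arm is an average, not a ceiling: early rows could hold more and pass more often.

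Finally, the trend term is no cure-all. For a 5-point fall, the size of the trial's own margin, its power is about 40% even with an even spread.

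None of this rescues the row-wise reading, which is what the legend says and which fails across the whole range of plausible row sizes.

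**Conclusion.** The concern holds in limited form. Applied by row, the stated reading would show failure for identical vaccines in about five of six sequence rows at 80 per arm and 90% seropositivity. The failure rate is 70% to 86% for true rates between 97% and 85%, and 69% to 91% for 160 down to 40 per arm at 90%. Passing all ten rows is practically impossible. It would be too strong to say that no single row can meet the margin; some will.

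The legend also conflicts with SAP 11.10, and the two need reconciling. If the sequence number is vial position, a decline with position is displayed but not tested, and the between-arm difference cannot detect one common to both arms. The primary analysis is untouched. The figures rest on the SAP's 800 evaluable infants per arm, equal true rates in both arms, and the row sizes shown.

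**What to change.** 1. Delete the non-inferiority legend from Tables 17.1.1.1 and 17.2.1.1, label both descriptive, and reconcile them with SAP 11.10.
2. Define Vaccination Sequential Number, and report how many infants fall at each value by arm.
3. Pre-specify one logistic model of day-91 seropositivity with sequence number as a linear term, estimated within each arm and adjusted for site, plus one arm-by-sequence interaction. Report both with 95% CI as exploratory.
4. State beside it that the trend has useful power only for large declines: about 86% for 95% to 85% and about 40% for 95% to 90% in one arm of 800 evenly spread, and less if late positions are sparse.

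The cost is SAP wording and one regression on data the SAP already tabulates.

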17.2. Sero-positivity at Day91: By Study Arm

17.2.1. Difference in Sero-positivity between study arms by Study Arm

Table17.2.1.1: Measles seropositive at day 91 post-vaccination (all infants) and difference in positivity between study arms by Study Arm

Seropositive at Day91 by Study arm	AER n/N	AER% 95% CI	SC n/N	SC% 95% CI	Difference (AER- SC) 95% CI
Vadu					
Pabal					
Talegaon					
Wagholi					
Nhavara					
Shel Pimpalgaon					
Chakan					
Alandi					

Legend: AER-aersol; SC-subcutaneous;

*This difference is used to interpret non-inferiority, estimated by Wilson score method.

SOP VEL 1/1:	Statistical Analysis Plan	Page 59 of 61
Sep 2012		

17.3. Comparison of baseline characteristics

17.3.1. Per – Protocol dataset

 Table 17.3.1.1: Comparison of baseline characteristics: Per-Protocol dataset

		Included s	Included subjects		Excluded Subjects* (with Reasons)	
		n	%	n	%	
Age in months	9.0-9.9					
Age in months	10.0-10.9					
	11.0-11.9					
Sev	Male					
	Female					
Health care	Govt.					
	Private					
	Non-gov					
	Other					
Pre-existing medical condition	Yes					
Tre-existing medical condition	No					
Significant illness in last 3 months	Yes					
Significant niness in fast 5 months	No					
DUC	Alandi					
i ne	Chakan					
	Nhavara					
	Pabal					
	Shel Pimpelgaon					
	Talegaon Dhevdhere					
	Vadu					
	Wagholi					
Seronositive at baseline	Yes					
	No					

SOP VEL 1/1:	Statistical Analysis Plan	Page 60 of 61
Sep 2012		

